6.3.3 Procedure to verify the diagnosis of PID (primary immunodeficiency)

Patients must have a well-documented PID (primary immunodeficiency) with impaired antibody production.

Data of examinations from primary medical records are taken into account. The scope of the conducted investigations and their sufficiency for differential diagnosis from other variants of immunodeficiencies is assessed.

The patient's history of treatment with immunoglobulin replacement therapy products is assessed (for previously treated patients).

Impaired antibody production in a patient can be demonstrated by the presence of diagnosis of primary immunodeficiency with obligate indications for replacement therapy (hereditary agammaglobulinaemia, hyper IgM syndrome, common variable immunodeficiency, severe combined immunodeficiency established according to ESID or WHO criteria, if such exist for them), low IgG levels (lower than 5 g/L) or impaired response to vaccines in other diagnoses of primary immunodeficiency.

In case of any doubts regarding the validity of the diagnosis, additional investigations are prescribed from a list previously agreed with the Sponsor.

6.3.4 Medical history, demographics, complaints and body weight measurement

During collection of medical history, the Investigator shall pay special attention to any direct and indirect findings that may suggest impossibility of including the patient into study. Any available medical records on comorbidities the patient might have and pharmacological and non-pharmacological treatments he/she is receiving must be analysed. Complete patient's history shall be reflected in source documents and in CRF. When taking a history, attention shall be paid to previous diseases, chronic comorbidities, heredity, habitual intoxications (smoking status, alcohol, drug use), allergy history, previous surgeries and injuries, clarification of occupational history,

permanent or periodic drug therapy. The patient's sex and age, as well as their race and ethnicity, are indicated in the source documentation. Body weight shall be measured using medical balances.

Anthropometric examinations shall be conducted in accordance with the Health Risk Monitoring (EHRM) Recommendations for indicators, international collaboration, protocol and manual of operations for chronic disease risk factor surveys, 2002 (European Health Risk Monitoring (EHRM), 2002).

Patients shall be weighed in the morning under fasting conditions, after urination and bowel movement, in their underwear (followed by deducting the average weight of clothing). The balances shall be positioned on a rigid base, horizontally. Measurement error shall not exceed 0.2 kg according to the standards. It is not allowed to write down body weight based on the patient's words, even in cases where body weight measurement is not possible.

Height measurement shall be performed in all patients (causes preventing height measurement include inability of the patient to stand, exceeding the scale of the stadiometer). Stadiometer – a vertically positioned board with centimetre markings and a sliding ruler – is used to determine height. The scale error shall not exceed 2 millimetres according to the standard. The patient is asked to remove their shoes, dense clothing, hairpins, and hairdo accessories. The patient must touch the vertical board with the back of their head, back, buttocks, calves, and heels, with the toes together. The upper edge of the external auditory canal opening must be at the same horizontal level as the lower edge of the orbit (zygomatic bone). The patient is asked to look straight ahead. The stadiometer ruler is lowered onto the head, and the markings are counted. Height is noted while the patient remains under the measuring visor. The error must not exceed half a centimetre.

The respective measurements for the paediatric population are performed according to the norms of the appropriate age-related category using the calibrated and metrologically verified measuring instruments.

Body mass index (BMI) will be calculated from the following formula:

$$BMI = \text{body weight (kg)} / (\text{height in m})^2$$

The eCRF shall capture information on disease onset, date of diagnosis, and review the source documentation regarding objective assessments on the basis of which the diagnosis was confirmed.

Information on comorbidities shall be recorded. Any drug products the patient was receiving within 3 months prior to onset of the study shall be documented in the CRF as a prior/concomitant treatment with reference to relevant indications, start date(s) and end date(s) of therapy.

6.3.5 Physical examination and vital sign measurements

Objective examination shall include auscultation of the heart and lungs, inspection of the skin and mucous membranes, abdominal palpation, measurement of HR, RR, BP and body temperature as well as other methods of physical examination according to current clinical situation. The data on the changes found during the examination shall be documented in the source documentation and in the eCRF.

Measurement of HR, RR, BP, and body temperature shall be conducted at rest (after 15 minutes of rest, not earlier than an hour after smoking cigarettes and 2 hours after eating). Heart rate (HR) shall be measured by auscultation of the heart in parallel with the determination of radial artery pulse rate (or carotid artery pulse rate if radial artery pulse is weak) per minute in the sitting position, both parameters shall be recorded in case of pulse deficit: HR and pulse rate. Respiratory rate (RR) shall be measured per minute at rest in the supine position with recording the respiratory movements of the chest or abdominal wall, without attracting the patient's attention.

Measurement of blood pressure (BP) will be performed in the brachial artery in the supine position by Korotkoff method using a certified sphygmomanometer or blood pressure monitor with cuff length and width suitable for patient's upper arm length and circumference. BP cuff size shall match the upper arm size: the rubber part of the cuff shall cover at least 80 % of the upper arm circumference; BP cuff of 12–13 cm wide and 30–35 cm long (average size) shall be used for adults; but availability of large- and small-size cuffs shall be required for large and small arms, respectively. The sphygmomanometer pointer must be at the zero mark before the start of measurement. To assess blood pressure levels in each arm, at least two measurements with intervals of at least 1 minute shall be performed; if BP difference is ≥ 5 mm Hg, one more additional measurement shall be performed on each arm; the minimum value of three measurements on the hand where the BP is higher shall be taken as the final (recorded) value.

Measurement method:

- Quickly inflate the air into the cuff to a pressure 20 mm Hg greater than systolic blood pressure (SBP) (estimated from the disappearance of the pulse);
- Measure BP with an accuracy of 2 mm Hg;
- Deflate the pressure in the cuff at a rate of approximately 2 mm Hg per 1 second;
- The pressure level at which the 1st sound appears corresponds to SBP (phase 1 of Korotkoff sounds);
- The pressure level at which the sounds disappear (Korotkoff phase 5) corresponds to dBp; when it is impossible to measure phase 5 in children, adolescents and young people immediately after exercise, and in adults in some pathological conditions, one shall attempt to identify Korotkoff phase 4, which is characterised by a significant weakening of the sounds;
- If the sounds are very weak, the patient shall be asked to raise the arm and perform several fist-clenching movements. After that, the measurement must be repeated; in doing so, the artery must not be strongly compressed with the diaphragm of the stethoscope;
- In initial examination of the patient, blood pressure shall be measured on both arms; subsequently, the measurements are performed on the arm where the BP is higher.

Temperature measurement is performed in the armpit using a medical thermometer (mercury thermometer), with the end of the thermometer, after shaking down, pressed firmly against the armpit by the upper arm; the skin in the armpit must be dry, because the thermometer shows a lower temperature if the skin is wet. The thermometer is kept in the armpit for 10–15 minutes. During the measurement, the patient must remain completely still.

Auscultation of the lungs and heart, palpation of the abdomen and examination of the skin and mucous membranes shall be carried out according to the standard procedure accepted in clinical practice for the screening phase, considering the general serious condition of patients. The objective of these procedures shall be to detect abnormal changes, including clinically significant ones. During the follow-up period, a less physically burdensome set of procedures shall be performed according to the standard procedure accepted in clinical practice, which allows assessment of the patient's condition.

The respective measurements for the paediatric population are performed according to the norms of the appropriate age-related category using the calibrated and metrologically verified measuring instruments (where applicable).

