4. STUDY DESIGN

4.1. Endpoints

Safety and tolerability endpoints

- Frequency of adverse events
- Incidence of adverse reactions to IMP
- Frequency of serious adverse reactions
- Emergence of treatment-emergent adverse events
- The frequency of treatment-emergent adverse events related to infusion rate
- The incidence of administration site reactions
- The frequency of clinically significant deviations in vital signs (blood pressure, body temperature, pulse rate and respiratory rate)
- The frequency of clinically significant deviations in laboratory findings (complete blood count, biochemical findings, markers of intravascular haemolysis, and coagulation parameters)

Safety data are also assessed separately in children and adolescents (after an interim assessment in adults) and compared with the adult data.

Primary pharmacokinetic endpoint:

Mean threshold (trough) plasma concentration of total IgG prior to the next administration of the product, when reaching steady state (after 4 months of treatment), assessed over 6 months.

Primary pharmacokinetic variable:

The monthly trough IgG levels, measured after 4 months of treatment with the IMP, prior to the next infusion, once every 4 weeks, over 6 months, did not fall below the trough levels of the previous therapy with SCIG or IVIG (BIOVEN).

Secondary pharmacokinetic endpoints

These endpoints are tested in the subgroup of subjects aged over 18 years who received treatment with BIOVEN prior to their enrolment in the study and, respectively, throughout the screening period:

- To confirm or calculate the IMP dose adjustment factor when converting from previous IVIG therapy with BIOVEN;

Tested in a subgroup of at least 20 adult patients with PID after approximately 4 months of treatment with the IMP BP-SCIG 20%:

- Area under the concentration-time curve (AUC)
- Maximum concentration (Cmax)
- Time to reach maximum concentration (Tmax)
- The threshold levels of total IgG during the dose titration phase (the dose-effect dependence)
- the *in vivo* elimination half-life
- the elimination constant
- serum clearance
- volume of distribution
- incremental recovery

Secondary endpoints are transformed into corresponding variables.

Primary efficacy endpoint:

Primary efficacy endpoint: The number of serious bacterial infections per subject per year (in order to achieve less than 1.0 infections/subject/year)

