Convert the variables measured on a continuous scale into categorical variables with the following two categories: “within normal” and “outside normal”. Perform an analysis of the converted variables using the methods of descriptive statistics (the frequency and percentage [%] in each group have been provided) and represent the distribution of categories as plots. Statistical inferences shall be made.

b) The results of HR, BP, RR and body temperature measurements.

Calculate descriptive statistics (n, arithmetic mean, standard deviation, the median and the percentiles, the minimum and maximum values – depending on the type of distribution) for each visit according to patient assessment schedule.

c) AE data.

Provide descriptive statistics (frequency and percentage for the group).

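### When a third blood-pressure reading is taken, Section 6.3.5 records the lowest of the three, which is biased low and not comparable with visits where no third reading is taken

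*Protocol*

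**What the plan says.** Section 6.3.5 asks that on each arm "at least two measurements with intervals of at least 1 minute shall be performed". It continues: "if BP difference is ≥ 5 mm Hg, one more additional measurement shall be performed on each arm". The final recorded value is then "the minimum value of three measurements on the hand where the BP is higher". For the period after the initial examination, when both arms are measured, the same section says: "subsequently, the measurements are performed on the arm where the BP is higher".

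The recorded value has two uses. Section 4.1 lists among the safety endpoints "The frequency of clinically significant deviations in vital signs (blood pressure, body temperature, pulse rate and respiratory rate"). Section 9.5(b) plans descriptive statistics by visit for "The results of HR, BP, RR and body temperature measurements", including mean, median, minimum and maximum.

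The protocol does not say:
- whether the 5 mm Hg difference is between successive readings or between the two arms;
- which value is recorded when no third reading is taken;
- whether the rule is applied separately to systolic and diastolic pressure;
- what numeric limit makes a blood-pressure deviation clinically significant.

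Nothing elsewhere in the protocol replaces the minimum by a mean or median.

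**The concern.** Repeated readings serve to reduce measurement error. Taking their minimum replaces random error with a systematic error in one direction. The rule also applies only when a difference is seen, so the shift is present at some visits and absent at others, and falls mostly on patients with variable readings.

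Two outputs are affected. The per-visit blood-pressure summaries mix values obtained under different rules. An investigator judging whether a deviation is clinically significant starts from a number that is sometimes the lowest of three readings and sometimes not. That judgement concerns a level rather than a change from baseline, so using the same rule at every visit would not cancel the shift. A later analysis can undo it only if the individual readings are kept, and the protocol does not say that they are.

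**Working it through.** The protocol states no figure for this rule, so there is none to reproduce. Its inputs are the 5 mm Hg trigger, the two initial readings and the minimum of three, all from Section 6.3.5. The within-visit SD, s, is an assumption, shown for 3 to 8 mm Hg. Readings are taken as independent and normal around the patient's true level.

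**Direction.** The minimum of three readings is never above their mean. If the difference is between the first two readings, the minimum is at most their average less half their difference, so it lies at least 5 / 2 = 2.5 mm Hg below that average. This needs no assumption about s.

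**If the difference is between readings (one fixed arm, as at later visits).**
- Probability of a third reading: the difference of two readings has SD s√2, so P = 2[1 - Φ(5 / (s√2))]. For s = 5, 5 / 7.07 = 0.707 and P = 0.48.
- Bias of the minimum: without the trigger, E[min of 3] = -0.846 s. Conditioning on a difference of at least 5 mm Hg makes it larger. The conditional values come from a simulation of 1,000,000 visits.
- Average over all visits, if two readings are otherwise averaged: P × conditional bias. For s = 5, 0.479 × (-5.44) = -2.61.

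| Assumed s (mm Hg) | Third reading | Bias when triggered (mm Hg) | Bias over all visits (mm Hg) |
|---|---|---|---|
| 3 | 24% | -3.9 | -0.9 |
| 4 | 38% | -4.7 | -1.75 |
| 5 | 48% | -5.4 | -2.6 |
| 6 | 56% | -6.3 | -3.5 |
| 8 | 66% | -7.9 | -5.2 |

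At triggered visits the mean and the median of the three readings both have a bias of about 0 for every s.

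At the initial examination both arms are measured, and choosing the higher arm offsets part of the shift. Simulation (500,000 examinations, s of 3, 5 and 8, true arm difference 0 or 5 mm Hg) gives -2.2 to -7.6 mm Hg, depending also on how the higher arm is identified.

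**If the difference is between arms.** The trigger is now that the two-reading means of the arms differ by at least 5 mm Hg. Bias when triggered, relative to the true level of the higher arm:

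| Assumed s (mm Hg) | True arm difference 0 | True arm difference 5 mm Hg |
|---|---|---|
| 3 | -0.8 | -1.7 |
| 5 | -1.9 | -3.0 |
| 8 | -3.5 | -5.05 |

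After the initial examination only one arm is measured, so this trigger could not occur again. Later visits would have two readings and no stated rule for the recorded value. The initial examination and the later visits would then be recorded differently.

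**The case against.** The strongest objection is the ambiguity. The sentence speaks of each arm and of the higher side, so a between-arms difference is a natural meaning. In that case on-treatment values would not be minima of three and the larger biases would not arise. This stands, and it is why the size is given for both meanings. It does not rescue the rule, because the initial examination would still be biased low and would differ in method from the visits that follow.

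A reader might infer that the safety tables will undercount high pressures and overcount low ones by a known amount. For example, at an SD of 5 mm Hg and with the between-readings trigger, a true value 5 mm Hg above a limit is recorded below it at 54% of triggered visits with the minimum, against 4% with the mean. The documents do not support that as a result. Section 4.1 counts clinically significant deviations and sets no numeric limit. The within-normal and outside-normal classification in Section 9.5 stands under laboratory results, not vital signs. Such percentages are illustrative only.

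A reader might also infer that the rule distorts detection of the abrupt fall in pressure that Section 2.3 names as a risk of the product. That does not follow either. Section 6.3.5 concerns a value taken at rest. Reactions to an infusion are covered by the observation rules in Section 6.1 and the adverse-event recording in Section 8.2, and from Cycle 2 three of every four infusions are given at home.

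Finally, no hypothesis test, sample size or stopping rule uses blood pressure. That is correct and limits the importance of the point.

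**Conclusion.** The point holds as a flaw in the recording rule. The direction of the bias is certain for single-arm readings and was negative in every two-arm variant examined. Its size is not fixed by the documents. It rests on an assumed within-visit SD of 3 to 8 mm Hg, on independent normal readings and on which meaning of the 5 mm Hg difference applies. The resulting bias is several mm Hg at a substantial share of visits if the difference is between readings, or a smaller one confined to the initial examination if it is between arms. Either way, values recorded with and without a third reading are not comparable. The consequence is limited to descriptive blood-pressure results and the judgements made from them, so this is a minor correction.

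**What to change.** In Section 6.3.5:
- state whether the 5 mm Hg difference is between readings on one arm or between arms, and reconcile the instruction to measure each arm with the single-arm rule for later visits;
- record the mean of all readings on the chosen arm, whether two or three, as the visit value at every visit, for systolic and diastolic pressure alike;
- use that value for the summaries in Section 9.5 and as the basis for judging deviations under Section 4.1.

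The cost is a sentence or two of protocol text. No extra measurement is needed, and sample size and formal analyses are unchanged.

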6.3.6 Chest X-ray/CT/MRI

Chest X-ray/CT/MRI is performed under a generally accepted procedure by a referral from the Investigator or the doctor who treated the patient prior to start of their participation in the clinical study. During the screening, this assessment is performed if not carried out during the last 6 months.

It is permitted to use of examination data obtained within the last 6 months prior to inclusion in the study.

6.3.7 Obtaining the results of quality of life questionnaires

According to the Schedule of Study Procedures, the Responsible Investigator/co-investigator provides the patient with a quality of life questionnaire to complete.

Adult patients will use the “Adult subject quality of life questionnaire” developed based on [name], PhD et al. Development and Initial Validation of a Questionnaire to Measure Health-Related Quality of Life of Adults with Common Variable Immune Deficiency: The CVID_QoL Questionnaire.

The procedure for filling in the “Adult subject quality of life questionnaire”:

1. The physician provides the questionnaire to the patient during the visit, to fill in Part I.
2. The patient completes the questionnaire by circling the scores corresponding to their condition.
3. The physician calculates the total score for each domain separately (psychological domain: 0–56 points; social domain: 0–36 points; clinical domain: 0–36 points).
4. A domain is not included in the assessment if more than 3 questions in it are left unanswered.
5. Calculation of Score for each domain is performed using the following formula:

$$x = \frac{\text{Sum of the scores for the domain} \times 100\%}{\text{Maximum sum of the scores for all items of the domain included in the analysis}}$$

$$\begin{aligned} & \text{Sum of the scores for the domain} \\ & = \text{the sum of all numbers in the domain circled by the patient.} \end{aligned}$$

$$\begin{aligned} & \text{Maximum sum of the scores for all items of the domain included in the analysis} \\ & = \text{the number of questions answered by the patient} \times 4 \end{aligned}$$

6. After the calculation, the physician records the result into the field for the respective domain (Part II).
7. The total score is calculated in a manner similar to assessment of each individual domain

$$x = \frac{\text{Sum of the scores for all domains} \times 100\%}{\text{Maximum sum of the scores for all items included in the analysis}}$$

8. After the calculation, the physician records the result into the Total Score field (Part II).

For paediatric patients (6–17 years), the “Quality of Life Questionnaire for Children and Adolescents” will be used, which was developed based on SCALING AND SCORING for the Acute and Standard versions OF THE Pediatric Quality of Life Inventory™ PedsQLTM.

Procedure of assessment on the “Quality of Life Questionnaire for Children and Adolescents”:

Step 1: Conversion of scores

Tasks are scored in reverse order and linearly transformed to a scale from 0 to 100 as follows:
0=100, 1=75, 2=50, 3=25, 4=0

Step 2: Scoring

Assessment by domains:

- If more than 50 % of the items in the scale are missing, the score for the scale in question is not calculated.
- Mean score = Sum of the scores for each item of the scale divided by the number of items answered by the respondent.

Summary score for psychosocial health = Sum of the scores for the emotional, social, and school functioning scales.

Summary score for physical health = score for the physical functioning scale.

Total score: Sum of the scores for all scales according to the number of responses to all items.

6.3.8 Bioanalytical procedures and laboratory investigations

The procedure is described in detail in the Laboratory Manual.

The following shall be collected as biological material: blood, urine.

The procedure for collection of biological material for laboratory tests is carried out at the clinical trial site or in a collection point (if, in the Investigator's judgement, the patient is mobile), or by a mobile team of a Sponsor-designated Central Laboratory.

Blood samples for analysis will be collected under fasting conditions (8–10 hours after the last meal) from a vein using a disposable sterile syringe, through a catheter or with a vacutainer, with adherence to aseptic/antiseptic precautions. Amount of blood taken shall be determined by the list of laboratory tests that need to be performed at the Visit (see Table 4.2.1).

For urinalysis, the middle portion of morning urine shall be collected after adequate perineal hygiene; the urine shall be delivered to the laboratory within two hours after collection.

Blood and urine samples for clinical analysis are collected under a standard procedure in accordance with the Laboratory Manual, according to the Schedule of Study Procedures (Table 4.2.1).

The procedures of preparation for analysis, collection, storage, transportation of biological material, and completion of accompanying documentation are carried out in accordance with the regulations described in the Laboratory Manual.

The list of Protocol-specified laboratory investigations:

- Complete blood count (haemoglobin, haematocrit, red blood cells, white blood cells and white blood cell differential, platelets);
- Serum chemistry (ALT, AST, creatinine, urea, glucose, total bilirubin);
- Blood test for HIV, RW, HBs-Ag, anti-HCV;
- Coombs' test (antiglobulin test);
- Haptoglobin level;
- Total serum IgG level;
- Urinalysis (specific gravity, pH, glucose; microscopic sediment examination – red blood cells, white blood cells, casts, crystals, bacteria, fungi);
- Pregnancy test (for women of childbearing potential);
- HIV test (express test), RW, HBs-Ag, anti-HCV;
- Glycated haemoglobin;
- Coagulation panel (INR, Prothrombin percentage by Quick, Prothrombin time, aPTT, fibrinogen);

